In nonclinical studies, venetoclax has demonstrated cytotoxic activity in tumor cells that overexpress BCL-2. Pre-clinical studies in T-ALL, particularly a high-risk subtype of early T-cell precursor acute lymphoblastic leukemia (ETP-ALL), using BH3 profiling, have revealed BCL-2 dependence with exquisite in vitro sensitivity to

the BCL-2-selective antagonist venetoclax.[20, 21]. Limited clinical experience also suggests that venetoclax is active against T-ALL.[22]

Venetoclax is highly bound to human plasma protein with unbound fraction in plasma <0.01 across a concentration range of 1-30 μ M (0.87-26 μ g/mL). The population estimate for the terminal elimination half-life of venetoclax was approximately 26 hours. The pharmacokinetics of venetoclax does not change over time.

Concomitant use of venetoclax with strong CYP3A inhibitors at initiation and during ramp-up phase is contraindicated. Concomitant use of venetoclax with strong CYP3A inhibitors increases venetoclax exposure (i.e., Cmax and AUC) and may increase the risk for tumor lysis syndrome at initiation and during ramp-up phase. For patients who have completed the ramp-up phase and are on a steady daily dose of venetoclax, reduce the venetoclax dose by at least 75% when strong CYP3A inhibitors must be used concomitantly.

Concomitant use of venetoclax with moderate CYP3A inhibitors or P-gp inhibitors should be avoided. If a moderate CYP3A inhibitor or a P-gp inhibitor must be used, reduce the venetoclax dose by at least 50%. These patients will be monitored more closely for signs of toxicities and will resume the venetoclax dose that was used prior to initiating the CYP3A inhibitor or P-gp inhibitor 2 to 3 days after discontinuation of the inhibitor.

2. Venetoclax will be obtained from commercial source and is the responsibility of the patient and/or insurance company. Study Population

Patients with relapsed/refractory acute myelogenous leukemia, high-risk myelodysplastic syndrome, or relapsed/refractory T-ALL/T-LBL.

3. Study Objectives

Primary Objectives

The primary objective of this study is to assess response rate as determined by the International Working Group recommendations in AML, MDS[23, 24] and in adult patients with relapsed/refractory T-ALL/T-LBL.

Secondary Objectives

The secondary objectives of this study are to assess:

- Safety and tolerability
- Time on treatment
- Overall survival
- Progression free survival

- Long-term response rate

Exploratory Objective

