13. Exclude patients with known Kell antibodies.

7. Dosage and Administration

Daratumumab will be administered at 16mg/kg for the first 2 Cycles (one time per week for 8 weeks) of treatment, followed by every 2 weeks for 4 cycles (or 16 weeks) and then every 4 weeks until progression or up to 1 year whichever comes earlier. All cycles are 4 weeks (28 days). The first visit of a cycle should be 4 weeks (+/- 3 days) after the start of the previous cycle, except in case of toxicities, see **Section 7B**. Every effort should be made to keep subjects on the planned dosing schedule.

Preparation

Infusion solution will be prepared as a 1000 mL (first dose) or 500-mL (second and subsequent doses) dilution of daratumumab in sterile, pyrogen-free 0.9% NaCl. Preparation of infusion bags should be done on the day of the planned infusion. Daratumumab must be administered as an IV infusion given through a well-functioning IV catheter by using an infusion pump (**Table 2**). The study drug must be filtered by using an inline filter (0.2 μ M) during the infusion. Manuals with detailed descriptions for preparation and administration of daratumumab will be supplied to pharmacy.

Venetoclax administration will follow following schedule for Cycle 1:

Table 1: Venetoclax dosing guidelines

	Day 1	Day2	Day3	Day 4-21
Not on mod/strong CYP inhibitor or Pgp inhibitor	100 mg	200 mg	400 mg	400 mg
On moderate CYP inhibitor or Pgp inhibitor	50 mg	100 mg	200 mg	200 mg
On strong CYP inhibitor excluding posaconazole	10 mg	20 mg	50 mg	100 mg

Receiving posaconazole	10 mg	20 mg	50 mg	70 mg
------------------------	-------	-------	-------	-------

For Cycle 2 onwards venetoclax will be dosed on days 1-21 at the dose intended to be administered on days 4-21 in cycle 1, but will start at that dose from Day1. Clinical judgement will be used to reduce the number of days of venetoclax administration based on disease status, ongoing clinically relevant issues e.g. infection, renal dysfunction etc.

Tumor lysis syndrome (TLS) prophylaxis during dose ramp-up of venetoclax will be per label of venetoclax for use in AML.

A. Treatment Schedule and Administration (Daratumumab)

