Subsequently, the infusion rate may be increased at the investigator's discretion.

If the intensity of the adverse event returns to Grade 3 or 4 after restart of the infusion, then the procedure described in this section may be repeated at the investigator's discretion. Should the intensity of the adverse event increase to Grade 3 for a third time, then the subject must be withdrawn from treatment. Any patient with grade 4 infusion related reaction at any time will be withdrawn from treatment.

F. Permitted Therapies

Use of hydroxyurea to control proliferative disease will be allowed prior to starting therapy on study and for up to 7 days (per cycle) during Cycles 1-3 (maximum daily dose of 7gm). Use of growth factors (G-CSF, GM-CSF and erythopoietic growth factors) will be permitted if considered to be in the best interest of the patient. Use of prophylactic/therapeutic antiemetics, antibiotics, antivirals and antifungals are permitted as per the decision of the treating physician. Prophylactic antiviral prophylaxis is recommended for all patients unless contraindicated.

G. Prohibited Therapies

Concomitant administration of investigational agents, including medications that target CD38, with the intention of treating AML/MDS are prohibited. Administration of commercially available agents with activity against or under investigation for AML/MDS/T-ALL (except hydroxyurea) should be avoided.

Concurrent use of corticosteroids is prohibited, unless used for prevention or treatment of infusion reactions (as above) or patients are on chronic steroids (maximum dose 20 mg/day prednisone equivalent) if they are being given for disorders other than treatment of AML/MDS, i.e., adrenal insufficiency, rheumatoid arthritis, etc.

H. Duration of Therapy

If a patient continues to respond or receive clinical benefit, he/she can continue treatment.

In the absence of treatment delays due to adverse event(s), treatment may continue once every four weeks (28 days) until one of the following criteria applies: disease progression or 1 year of treatment whichever is earlier.

8. Study Procedures

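### Section 1 contraindicates strong CYP3A inhibitors at venetoclax initiation and ramp-up, but Table 1 schedules Day 1-3 ramp-up doses for patients taking them

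*Combined protocol and SAP*

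**What the plan says.** **Section 1, Background (Venetoclax).** The rule for strong inhibitors carries no exception: "Concomitant use of venetoclax with strong CYP3A inhibitors at initiation and during ramp-up phase is contraindicated". The stated reason is higher venetoclax exposure and a possible increase in tumor lysis risk during that phase. A second rule follows for a later phase. Its scope is "For patients who have completed the ramp-up phase and are on a steady daily dose of venetoclax", and its instruction is to "reduce the venetoclax dose by at least 75% when strong CYP3A inhibitors must be used concomitantly".

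**Section 7, Dosage and Administration.** Table 1 is introduced by "Venetoclax administration will follow following schedule for Cycle 1". Its reference row is "Not on mod/strong CYP inhibitor or Pgp inhibitor". Two further rows concern strong inhibition: "On strong CYP inhibitor excluding posaconazole" and "Receiving posaconazole". Both give doses from Day 1.

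**Other places that bear on the point.**
- Section 6 (Eligibility Criteria) and Section 7.G (Prohibited Therapies) do not mention CYP3A inhibitors.
- Section 7.F (Permitted Therapies) says that "antivirals and antifungals are permitted as per the decision of the treating physician", with no CYP3A condition attached.
- Section 5 (Study Design) and Section 11 (Statistical Considerations) refer venetoclax dosing to the package insert for AML, which the protocol does not reproduce.

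**The concern.** On the first three days of venetoclax, Section 1 says the combination must not be given and Table 1 says how to give it. A pharmacist or monitor working from Section 1 could withhold treatment that Table 1 provides for, or record Table 1 dosing as a deviation. An investigator working from Section 7 would dose without knowing that the same protocol contraindicates the combination.

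Section 1 itself ties this period to tumor lysis, which Section 13.B lists as an adverse event of special interest. The instruction for these days should therefore be free of contradiction. At stake are consistent conduct at treatment start and a clear answer on whether a patient already taking such a drug may begin venetoclax.

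**Working it through.** This is a comparison of texts, with short arithmetic to fix where the conflict begins and ends. The plan gives no figure of its own to reproduce.

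**1. Do the two places speak of the same drugs?** Section 1 says CYP3A; Table 1 says only CYP. Section 1 names no other CYP class, and Table 1 uses the same strong, moderate and P-gp groups, so the same drugs are meant. Table 1 excludes posaconazole from its strong-inhibitor row in order to give it a separate row, which implies that the protocol counts it as a strong inhibitor.

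**2. Do they speak of the same days?** Table 1 covers Cycle 1, and Section 7 refers to the venetoclax ramp-up directly below it. In both strong-inhibitor rows the dose rises on each of Days 1-3 and reaches its final level in the Day 4-21 column. Days 1-3 are therefore initiation and ramp-up. From Cycle 2, Section 7 starts at the Day 4-21 dose with no new ramp.

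**3. Reduction against the no-inhibitor row.** Inputs are the mg doses in Table 1. Formula: reduction = 1 − (dose in row ÷ dose in no-inhibitor row).

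| Days of Cycle 1 | No inhibitor | Strong, not posaconazole | Posaconazole |
|---|---|---|---|
| Day 1 | 100 | 10: 1 − 10/100 = 90% | 10: 90% |
| Day 2 | 200 | 20: 1 − 20/200 = 90% | 20: 90% |
| Day 3 | 400 | 50: 1 − 50/400 = 87.5% | 50: 87.5% |
| Days 4-21 | 400 | 100: 1 − 100/400 = 75% | 70: 1 − 70/400 = 82.5% |

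**4. Comparison with Section 1.**
- *Days 4-21.* Section 1 requires a cut of at least 75%, so at most 0.25 × 400 = 100 mg. Table 1 gives 100 mg and 70 mg. The two places agree.
- *Days 1-3.* The cuts all exceed 75%, but that does not bring them within Section 1. Its dose-reduction rule is limited to patients past ramp-up. For the earlier phase it states a contraindication, which a reduced dose does not satisfy.

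**5. Does any other text settle it?** Sections 6 and 7.G contain no bar on these drugs, and Section 7.F leaves antifungals to the physician. The package-insert references in Sections 5 and 11 add a third source without ranking it. Nothing limits the Section 1 statement to another indication, and nothing says that Table 1 overrides it.

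**The case against.** The best reply is that Section 1 is background and Section 7 is the operative text. Table 1 names strong inhibitors and posaconazole explicitly and gives a definite schedule. The silence of Sections 6 and 7.G and the permission in Section 7.F are consistent with it. A site dosing from Section 7 would know what to do. Table 1 also already reduces the disputed doses by 87.5% to 90%. The protocol adds tumor lysis prophylaxis during ramp-up (Sections 5 and 7) and excludes patients with a white cell count above 25 × 10⁹/L before venetoclax (Section 6.B).

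Much of this stands. Table 1 is the working schedule, and these safeguards belong in any account of tumor lysis risk. But that Section 7 prevails is the reader's inference, since the protocol states no order of precedence. An unqualified contraindication remains in the same document.

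Four stronger readings are tempting, and the documents do not support them:
- *That the Section 1 contraindication is plainly study instruction because it says patients will be monitored more closely.* That sentence belongs to the paragraph on moderate CYP3A and P-gp inhibitors. The directive in the strong-inhibitor paragraph is the 75% reduction, which applies only after ramp-up.
- *That the toxicity stopping rule is compromised.* The rule in Section 11 counts treatment-related grade 3 or higher non-hematologic toxicities within 12 weeks. It does not measure exposure, and no boundary or operating characteristic depends on this point.
- *That a known share of the 36 patients is affected.* The documents give no frequency of strong-inhibitor use and nothing from which to estimate one.
- *That the Table 1 doses are shown to be wrong.* The conflict does not show which statement is at fault.

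**Conclusion.** The contradiction holds as an internal inconsistency in clinical instructions. It covers venetoclax initiation and Days 1-3 of Cycle 1, for patients on a strong CYP3A inhibitor or posaconazole. It does not extend to Days 4-21 or to later cycles, where Table 1 and Section 1 agree. The sample size, priors, stopping boundaries and operating characteristics are unaffected.

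The conclusion rests on two readings: that Table 1's CYP inhibitors are Section 1's CYP3A inhibitors, and that ramp-up means Days 1-3 as Table 1 is laid out. The wording and structure of the protocol support both. The point should be corrected because it concerns a period that the protocol links to tumor lysis, but the existence of one definite dosing table limits its weight.

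**What to change.** Reconcile the strong-inhibitor text in Section 1 with Table 1 in Section 7, together with the package-insert references in Sections 5 and 11. One instruction should then apply to starting and ramping venetoclax in a patient on a strong CYP3A inhibitor or posaconazole. The sponsor's clinical team must decide which statement stands; this review takes no position on that.

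Once that is decided:
- align Sections 6, 7.F and 7.G with the chosen instruction;
- use the same drug-class term in Section 1 and Table 1;
- state which text governs if the protocol and the package insert differ.

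The cost is protocol wording only. No statistical quantity needs to be recalculated.

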The criteria for a dose delay are as follows:

Grade 3 or higher non-hematologic toxicities with the following exceptions:

- Grade 3 nausea that responds to antiemetic treatment within 7 days
- Grade 3 vomiting that responds to antiemetic treatment within 7 days
- Grade 3 diarrhea that responds to antidiarrheal treatment within 7 days
- Grade 3 fatigue that was present at baseline or that lasts for <7 days after the last administration of daratumumab
- Grade 3 asthenia that was present at baseline or that lasts for <7 days after the last administration of daratumumab
- isolated Grade 3 or higher glutamyltransferase elevation

If daratumumab administration does not commence within the prespecified window (**Table 3**) of the scheduled administration date (either for toxicity or extenuating circumstances), then the dose will be considered a missed dose. Administration may resume at the next planned dosing date.

Table 3. Daratumumab-related Toxicity Management

Cycles	Frequency	Dose Miss	Dosing Resumption
1 -2	Weekly (Q1W)	>3 days	next planned weekly dosing date

3-6	Every 2 weeks (Q2W)	>7 days	next planned every 2 weeks dosing date
7+	Every 4 weeks (Q4W)	>14 days	next planned every 4 weeks dosing date

A missed dose will not be made up. **If a dose is delayed (beyond the usual permissible window), then the dates of all subsequent doses must be adjusted.** Any adverse event deemed to be related to daratumumab that requires a dose hold of more than 4 weeks (Cycle 1 to Cycle 6) or more than 6 weeks (Cycle 7 and beyond) will result in permanent discontinuation of daratumumab.

Interruption or Missed Doses

Subjects missing ≥ 3 consecutive planned doses of daratumumab for toxicity related to daratumumab should be withdrawn from the study. For subjects missing ≥ 3 consecutive planned doses of daratumumab with reasons other than toxicity should also be withdrawn, unless upon consultation with the IND office and review of the safety and efficacy, continuation is agreed upon.

b. Venetoclax:

Venetoclax dose reduction will follow its dose modification suggestions in acute myeloid leukemia from its package insert.

Additional dose reductions and delays are allowed for venetoclax in cycle 1 and subsequent cycles if considered in the best interest of the patient and based on expertise of the investigator.

C. Pre-infusion medication (Daratumumab)

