need to be reported on unscheduled case report forms. Subjects who experience adverse events during the infusion must be treated according to the investigator's judgment and best clinical practice. The following guidelines apply:

- Subjects should be treated with acetaminophen, H1-antihistamine, or corticosteroids as needed. Intravenous saline may be indicated. For bronchospasm, urticaria, or dyspnea, subjects may require H1-antihistamines, oxygen, corticosteroids, and/or bronchodilators. For hypotension, subjects may require vasopressors.
- In the event of a life-threatening infusion-related reaction (which may include pulmonary or cardiac events) or anaphylactic reaction, daratumumab should be discontinued and after consultation with the supporter's and/or IND office's medical monitor, no additional daratumumab should be administered to the subject. Aggressive symptomatic treatment should be applied. If an infusion is paused, then a longer-than-anticipated infusion time may occur. Overnight stays at the hospital because of slow infusion times should not be reported as a serious adverse event.

Infusion-Related Reactions of Grade 1 or Grade 2

For infusion related adverse events that are Grade 1 or 2, the infusion should be paused. When the subject's condition is stable, the infusion may be restarted at the investigator's discretion. Upon restart, the infusion rate should be half of that employed before the interruption. Subsequently, the infusion rate may be increased at the investigator's discretion.

If the subject experiences a Grade 2 or higher event of laryngeal edema, or a Grade 2 or higher event of bronchospasm that does not respond to systemic therapy and does not resolve within 6 hours from onset, then the subject must be withdrawn from treatment.

Infusion-Related Reactions of Grade 3 or Higher

For infusion-related adverse events that are Grade 3 or higher, the infusion must be stopped and the subject must be observed carefully until resolution of the adverse event. If the intensity of any other adverse event remains at Grade 3 after 2 hours, then the subject must be withdrawn from treatment. Any patient with grade 4 infusion related reaction will also be withdrawn from treatment. If the intensity of any other adverse event decreases to Grade 1 or 2 within 2 hours, then the infusion may be restarted at the investigator's discretion. Upon restart, the infusion rate should be half of that employed before the interruption.

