state or marrow CR within 12 weeks of treatment. The method of Thall, Simon and Estey[26] will be used to monitor efficacy and safety. The design software Multc Lean Desktop (version 2.1) developed by the Department of Biostatistics at M. D. Anderson Cancer Center (MDACC) was used to generate the stopping boundaries and the operating characteristics table for futility and toxicity monitoring.

Futility

We assume a target response rate of 25% and a response rate of 15% or lower will be considered not desirable. The study will be stopped early if the data suggest that:

$$\Pr(P_E > P_H + 0.10 | \text{data}) < 0.025$$

where P_E and P_H are the response rates for daratumumab in combination with venetoclax and historical treatment, respectively. That is, if at any time during the study we determine that there is less than 2.5% chance that the response rate improves over historical rate by more than 10%, the trial will be stopped due to futility. P_E and P_H are assumed to follow a prior of Beta (0.3, 1.7) and Beta (150, 850), respectively. The stopping boundaries for efficacy based on these assumptions and monitoring conditions are provided in **Table 4**. We will apply these stopping boundaries in cohort sizes of 6.

Table 4. Stopping boundaries for futility monitoring

# of patients evaluated for response	Stop the trial if # of patients with response is less than or equal to:
6-12	0
18	0-1
24	0-2
30	0-3
36	0-4

Toxicity

Unacceptable toxicities are defined as any treatment-related grade 3 or higher non-hematologic toxicities that occur within the first 12 weeks of treatment. Denote the probability of toxicity by P_T . We assume as a priori, $P_T \sim \text{beta}(0.6, 1.4)$. Our stopping rule is given by the following probability statement:

$$\Pr(P_T > 0.30 | \text{data}) > 0.975.$$

That is, we will stop the trial for new patient enrollment if at any time during the study, we determine that there is more than 97.5% chance that the unacceptable toxicity rate is more than 30%. This toxicity monitoring rule will be applied after the first 6 patients have been enrolled and evaluated, and then in cohort size of 6. Stopping boundaries corresponding to this stopping rule are listed in **Table 5**. The operating characteristics for efficacy and toxicity monitoring are summarized in **Table 6**.

Table 5. Early stopping boundaries for toxicity monitoring

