# of patients (in cohort size of 6, starting from the 6 th patient)	Stop the trial if there are this many patients with toxicities:
6	5-6
12	8-12
18	10-18
24	13-24
30	15-30
36	17-36

Table 6. Operating characteristics for efficacy and toxicity monitoring

True response rate	True toxicity rate	Prob (stop the trial early)	Average number of patients treated
0.15	0.10	0.5752	25.3
	0.30	0.5959	24.7
	0.40	0.7049	22.3
	0.50	0.8895	17.3
0.25	0.10	0.2119	35.0
	0.30	0.2504	34.1
	0.40	0.4526	30.2
	0.50	0.7950	22.3
0.30	0.10	0.1282	37.6
	0.30	0.1708	36.6
	0.40	0.3945	32.3
	0.50	0.7732	23.6

Analysis Plan

Summary statistics will be provided for continuous variables and frequency tables will be used to summarize categorical variables. We will estimate the overall response rate, along with the Bayesian 95% credible interval. Kaplan-Meier method will be used to estimate overall survival, time to treatment and progression-free survival. The two-sided log-rank tests will be used to assess the differences of time-to-event outcomes between subgroups of patients. Logistic regression analyses will be used to explore the association between biomarker and response or resistance to therapy.

Data from all subjects who receive any study drug will be included in the safety analyses. Subjects who entered the study but did not take any of the study drug and had this confirmed will not be evaluated for safety. The severity of the toxicities will be graded according to the NCI CTCAE v4.03 whenever possible. We will follow standard reporting guidelines for adverse events. Safety data will be summarized by category, severity and frequency.

12. Adverse Events and Reporting Requirements

Adverse event reporting will be as per the current NCI criteria and the Leukemia-specific Adverse Event Recording and Reporting Guidelines (Appendix D) . The descriptions and grading scales found in the revised NCI Common Terminology Criteria for Adverse Events (CTCAE) version 4.03 will be utilized for adverse event reporting.

<http://ctep.cancer.gov/reporting/ctc.html>

A. Adverse Events

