The type of birth control used must be discussed with, and approved by, the study doctor before beginning the study. Approved birth control must be in the form of oral, injected or implanted methods (e.g., placement of an intrauterine device or intrauterine system, condom with spermicidal foam/gel/film/cream/suppository, diaphragm, cervical/vault caps with spermicidal foam/gel/film/cream/suppository, male partner sterilization, or abstinence).

All initial reports of pregnancy must be reported to Janssen Scientific Affairs, LLC by the PRINCIPAL INVESTIGATOR within 24 hours of becoming aware of the event using the Serious Adverse Event Form. Abnormal pregnancy outcomes (e.g. spontaneous abortion, fetal death, stillbirth, congenital anomaly, ectopic pregnancy) are considered serious adverse events and must be reported using the Serious Adverse Event Form.

Any subject who becomes pregnant during the study must be promptly withdrawn from the study and discontinue further study treatment.

Because the effect of the Janssen medicinal product on sperm is unknown, pregnancies in partners of male subjects exposed to a Janssen medicinal product will be reported by the PRINCIPAL INVESTIGATOR within 24 hours of their knowledge of the event using the Serious Adverse Event Form. Depending on local legislation this may require prior consent of the partner.

Follow-up information regarding the outcome of the pregnancy and any postnatal sequelae in the infant will be required.

F. Maintenance of Safety Information

All safety data should be maintained in a clinical database in a retrievable format. The PRINCIPAL INVESTIGATOR shall provide all adverse events, both serious and non-serious, in report format. However, in certain circumstances more frequent provision of safety data may be necessary, e.g. to fulfill a regulatory request, and as such the data shall be made available within a reasonable timeframe at Janssen Scientific Affairs, LLC request.

G. Procedures for Reporting Safety Data and Product Quality Complaints (PQCs) for Janssen Medicinal Products to Janssen Scientific Affairs, LLC

All adverse events and special situations, whether serious or non-serious, related or not related, following exposure to a Janssen medicinal product are to be documented by the investigator and recorded in the CRF and in the subject's source records. Investigators must record in the CRF their opinion concerning the relationship of the adverse event to a Janssen medicinal product.

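### Section 7.B withdraws patients from the study, not from treatment, after three consecutive missed daratumumab doses, and no rule says how those who leave before week 12 count for response

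*Combined protocol and SAP*

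**What the plan says.** Section 7.B (Interruption or Missed Doses) says that subjects missing three or more "consecutive planned doses of daratumumab for toxicity related to daratumumab should be withdrawn from the study". Subjects missing as many for other reasons "should also be withdrawn, unless upon consultation with the IND office and review of the safety and efficacy, continuation is agreed upon".

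Other stopping rules use different terms. Earlier in Section 7.B, a related event needing a hold of more than 4 weeks (Cycles 1-6) or more than 6 weeks (Cycle 7 on) "will result in permanent discontinuation of daratumumab". For infusion reactions that do not settle, Section 7.E says "then the subject must be withdrawn from treatment". Section 13.E says that a subject who becomes pregnant "must be promptly withdrawn from the study and discontinue further study treatment", which names the two acts separately.

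Section 11 defines the primary endpoint as response within 12 weeks of treatment. Table 4 applies the futility rule to the number of patients evaluated for response. The term is not defined, no response population is given, and no rule covers a patient who leaves before week 12 without an assessment. For safety the set is explicit: "Data from all subjects who receive any study drug will be included in the safety analyses". Section 8 has an End of Treatment visit after discontinuation for any reason, with assessments at the investigator's discretion, followed by survival calls.

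**The concern.** Three stopping terms are in use and none is defined. A site that takes Section 7.B at its word would treat the patient as off study, while a patient stopped under Section 7.E would be off treatment only. The patients concerned are selected by toxicity or by failure to stay on schedule, so they are unlikely to resemble the rest.

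The main exposure is the primary endpoint. If these patients have no response marrow and drop out of the evaluated count, the response rate rises and the futility rule sees a smaller denominator. The second exposure is uncertainty about survival contact and late toxicity collection once a patient is off study.

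**Working it through.** **1. When the rule acts.** Inputs: dosing intervals of 7, 14 and 28 days (Section 7.A), missed-dose limits of more than 3, 7 and 14 days (Table 3), and the hold limits of 4 and 6 weeks (Section 7.B). Time from the last dose given to the third missed dose:

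- Cycles 1-2: 3 × 7 = 21 days, plus the 3-day limit = 24 days, under the 28-day hold limit. The study-withdrawal rule comes first.
- Cycles 3-6: 3 × 14 = 42 days, over 28. The daratumumab-discontinuation rule comes first.
- Cycle 7 on: 3 × 28 = 84 days, over 42. Discontinuation again comes first.

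For toxicity, then, the wording acts mainly in Cycles 1-2. A patient dosed on Day 1 who misses Days 8, 15 and 22 has the third miss confirmed once Day 25 has passed. The first on-treatment marrow is Cycle 2 Day 1, which is Day 29, or Day 27 at the earliest with the 2-day window. If the last three weekly doses of Cycle 2 are missed (Days 36, 43 and 50), the point is Day 53. Twelve weeks end on Day 84.

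**2. Toxicity.** A toxicity hold requires an event related to daratumumab that meets "Grade 3 or higher non-hematologic toxicities with the following exceptions". The monitored endpoint is: "Unacceptable toxicities are defined as any treatment-related grade 3 or higher non-hematologic toxicities that occur within the first 12 weeks of treatment". The exceptions only narrow the hold criteria, so every event that triggers a hold within 12 weeks is already a counted toxicity. What could be lost is a later new event. Table 7 collects adverse events to 30 days after the last dose of the last study drug. In the example above, if venetoclax ended on Day 21, that is Day 51, which leaves 84 − 51 = 33 days of the toxicity window. Related serious events after 30 days must still be reported (Section 12.B), so the gap concerns new non-serious events.

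**3. The plan's own boundaries.** With P_E ~ Beta(0.3 + x, 1.7 + n − x) for x responders among n, and P_H ~ Beta(150, 850), the trial stops if Pr(P_E > P_H + 0.10 | data) < 0.025. Numerical integration over P_H reproduces every boundary in Table 4: 0, 0, 1, 2, 3 and 4 at n = 6, 12, 18, 24, 30 and 36.

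**4. Effect of dropping unassessed non-responders on the futility rule.**

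| All treated | Posterior | Some dropped | Posterior |
|---|---|---|---|
| 0/6 | 0.0192, stop | 0/5 (one dropped) | 0.0275, continue |
| 1/18 | 0.0089, stop | 1/14 (four dropped) | 0.0261, continue |
| 2/24 | 0.0122, stop | 2/20 (four dropped) | 0.0311, continue |
| 3/30 | 0.0136, stop | 3/27 (three dropped) | 0.0257, continue |
| 4/36 | 0.0138, stop | 4/32 (four dropped) | 0.0302, continue |

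At the first look one exclusion is enough to remove the trigger, or to delay it until another patient is evaluated. From n = 18 on it takes three or four. At n = 12 with no responder, any evaluated number from 6 to 12 still stops, so seven would have to be dropped.

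**5. Effect on the estimate.** The documents give no withdrawal rate, so 1 to 6 dropped non-responders is an assumption. The 95% credible interval is from Beta(0.3 + 9, 1.7 + n − 9).

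| Dropped | Rate | 95% credible interval |
|---|---|---|
| 0 | 9/36 = 25.0% | 12.4% to 39.1% |
| 1 | 9/35 = 25.7% | 12.7% to 40.1% |
| 3 | 9/33 = 27.3% | 13.5% to 42.1% |
| 6 | 9/30 = 30.0% | 15.0% to 45.6% |

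The undesirable and target rates, 15% and 25%, are 10 points apart.

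**The case against.** A reader might infer that the rule takes toxicity failures out of toxicity monitoring and survival follow-up. The documents do not support that. The triggering event is already counted (step 2), and the safety set keeps everyone dosed. Events ongoing when a subject stops the study are followed (Section 8, Follow-up Period), as are serious events unresolved when participation ends (Section 13.H). Discontinuation for any reason leads to the End of Treatment visit, and the survival calls that follow exclude nobody by reason for stopping. Section 13.E also asks for pregnancy outcome after a subject has left, so study withdrawal in this protocol does not plainly mean that data collection ends. All of this stands, and it suggests that the sponsor means to keep following these patients.

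A reader might also infer a biased survival curve. Assume 10% withdrawn and censored at 2 months with a residual median of 2 months, and a median of 7 months in the rest. Kaplan-Meier would then read 56.4% against a true 52.2% at 6 months, and 31.1% against 27.7% at 12 months. None of these inputs is in the documents, and the calculation assumes that contact ends, which is the open question. It is an illustration on assumptions only and carries no weight in the conclusion.

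It is fair to add that the undefined response denominator affects any early exit, whatever Section 7.B says. That is true, and the fix has to cover it. Section 7.B still adds to the problem, because its literal wording is a reason to stop assessing response, and no rule then says how the patient counts.

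**Conclusion.** The concern holds for response and, as an ambiguity, for survival contact and late toxicity collection. It does not hold for the triggering toxicity or the safety set. The stopping terms in Sections 7.B, 7.E and 13.E are not reconciled. Read literally, mainly in Cycles 1-2, Section 7.B may end response assessment inside the primary window.

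The size depends on how many patients leave unassessed and whether they are dropped, and the documents state neither. For one to six dropped non-responders, an observed 25.0% would read 25.7% to 30.0%. One exclusion can switch off or delay futility stopping at the first look; from n = 18 on it takes three or four. This should be corrected before the response analysis, and it is cheap to do.

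**What to change.** 1. Reconcile the stopping terms in Sections 7.B, 7.E and 13.E and define each one, without changing which drug stops or when. The clinical rules themselves are for the sponsor and investigator.
2. State that patients who stop treatment under Section 7.B remain in safety, 12-week response and survival follow-up unless they withdraw consent, and that toxicity is collected to week 12 for the monitoring rule.
3. In Section 11, define the response population as all treated patients, for both Table 4 and the final estimate. Count those who leave unassessed before week 12 as non-responders, whatever the reason for leaving.

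The cost is a few sentences. The survival calls are already in Section 8 and Table 7, and the boundaries in Tables 4 and 5 do not change. Some patients who are off treatment would need a response assessment and a toxicity contact up to week 12. The downside is that the reported response rate may be slightly less favourable.
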